7.2. Clinical Laboratory Data

All laboratory results will be standardized by converting values in original units to values in standard units and classified as normal, abnormal low, or abnormal high on normal ranges supplied by the local laboratories and upon employing standardization.

When a certified local laboratory is used instead of a central laboratory due to COVID-19 pandemic, the units and normal ranges might be different. Therefore, all local laboratory values will be standardized to a central laboratory value using the following formula:

$$X_S = L_S + \frac{U_S - L_S}{U_X - L_X} \times (X - L_X)$$

Where,

X: local lab value

 $X_{\rm S}$: standardized value of X

 $L_{\rm S}$: Low normal range for central lab

 U_S : High normal range for central lab

 L_X : Low normal range for local lab

 U_X : High normal range for local lab

Specifications will be developed to detail all the steps necessary for developing the standardized laboratory values and to address issues like missing normal ranges or negative standardized laboratory values.

Observed and change from baseline of clinical laboratory data (hematology, serum chemistry, coagulation and continuous urine chemistry parameters) will be summarized at each analysis visit by treatment group and overall. Categorical urine chemistry data will also be tabulated at each analysis visit when applicable.

In addition, liver abnormalities will be summarized at each analysis visit including following variables by treatment group and overall:

- ALT or AST $\geq 3 \times ULN$
- ALT or AST \geq 3×ULN and (TBL \geq 2×ULN or INR \geq 1.5)
- ALT or AST \geq 5×ULN
- ALT or AST >8×ULN

Clinical laboratory test values are potentially clinically significant (PCS) if they meet either the low or high PCS criteria listed in the table below:

Table 2: Criteria for Potentially Clinically Significant Laboratory Tests

Parameter	Criteria
Hematology	
WBC (total) (x10^9/L)	< 3.0 > 16
Lymphocyte (x10^9/L)	< 0.5 < 0.8 > 12
Neutrophils (x10^9/L)	< 1.0 < 1.5 > 12
RBC (x10^12/L)	< 3.3 > 6.8
Hemoglobin (g/dL)	< 10
Platelet count (x10^9/L)	< 100 > 600

Table 2: Criteria for Potentially Clinically Significant Laboratory Tests

Parameter	Criteria
Serum Chemistry	
ALT	> 1.5xULN > 3.0xULN
AST	> 1.5xULN > 3.0xULN
ALP	> 1.5xULN > 3.0xULN
Total Serum Bilirubin	> 1.5xULN
GGT	> 3.0xULN
ALT or AST > 3xULN and concurrent elevated total bilirubin defined as	> 2.0xULN

For the following serum chemistry parameters: creatinine; LDH; creatine kinase (CK); uric acid; glucose; sodium; potassium; and chloride, abnormal values will be used as potentially clinically significant.

The number and percentage of participants with post-baseline PCS laboratory values will be tabulated by treatment group and overall. A listing of participant data with at least one post-baseline PCS value will be provided.

All laboratory values will be listed for each participant.

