13.4. Definition of Analysis Visit Windows

Unless otherwise specified, the actual scheduled nominal post-baseline visit will be used for all summaries across time. Post-baseline unscheduled visits, follow-up visits, and early termination visits will be mapped to a scheduled visit and will be used in the analysis only if the nominal scheduled visit result is missing. Table 5 presents the analysis visit window mapping for unscheduled and early term visits for assessments done mostly every 4 weeks (central lab, vital sign, PK). For other assessments that do not follow Table 5 schedule (such as 24-hour urine, triplicate FMU uPCR, ECG, PD, ADA, etc.), the analysis visit window mapping will be adjusted accordingly. In the case that multiple unscheduled or early termination visits are in the same analysis window, the one closest to the target date will be used. In the event that the windowed visit is mapped to an illogical sequence of visits when considering nearby scheduled visits (ie, windowed visit is higher than the subsequent visit or lower than the preceding visit), the windowed visit will be set to the logical scheduled visit.

Table 5: Analysis Visit Windows for Unscheduled and Early Termination Visits for Assessments Done Mostly Every 4 Weeks

Study period	Analysis visit	Target day	Analysis window	Interval					
Screening	Week -10 to -4	-49	-77 - < -21	56					
	Week -2	-14	- 21 - ≤ - 1	21					
Randomized	Day 1	1	1	1					
controlled period	Week 4	28	2-<42	40					
P	Week 8	56	42 - < 70	28					
	Week 12	84	70 - < 98	28					
	Week 16	112	98 – < 126	28					
	Week 20	140	126 – < 154	28					
	Week 24	168	154 – < 175	21					
	Week 26	182	175 – < OLP start date	NA					
Open-label period	Week 28	196	OLP start date – <210	NA					
	Week 32	224	210 - < 238	28					
	Week 36	252	238 – < 273	35					
	Week 42	294	273 – < 315	42					
	Week 48	336	315 - < 350	35					
	Week 52 (for roll-over participants)	364	350 – < 434	84					
	Week 52 (for non-roll- over participants)	364	350 – < 371	21					

Table 5: Analysis Visit Windows for Unscheduled and Early Termination Visits for Assessments Done Mostly Every 4 Weeks

Study period	Analysis visit	Target day	Analysis window	Interval
Follow-up	Week 54	378	371 – < 385	14
period (for participants	Week 56	392	385 – < 406	21
not entering long term extension)	Week 60	420	406 – < 434	28

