13.5. Repeated or Unscheduled Assessments of Safety Parameters

For safety parameters, if a participant has repeated assessments before the start of investigational product, then the results from the final assessment made prior to the start of investigational product will be used as baseline. If end of study assessments are repeated or unscheduled, the last post-baseline assessment will be used as the end of study assessment for generating descriptive statistics. However, all post-baseline assessments will be used for Potentially Clinically Significant (PCS) value determination and all assessments will be presented in the data listings.

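### SAP 7.2 specifies no any-time participant count for ALT/AST ≥5×ULN, >8×ULN or the INR-based liver criterion, and unscheduled peaks can drop out of the by-visit liver table

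*SAP*

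**What the plan says.** SAP 7.2 (Clinical Laboratory Data) states that "liver abnormalities will be summarized at each analysis visit including following variables by treatment group and overall". Four categories follow: ALT or AST ≥3×ULN; ALT or AST ≥3×ULN with total bilirubin (TBL) ≥2×ULN or INR ≥1.5; ALT or AST ≥5×ULN; and "ALT or AST >8×ULN". No worst-value or any-time row is mentioned.

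SAP 13.4 sets the source of by-visit tables: "the actual scheduled nominal post-baseline visit will be used for all summaries across time". Post-baseline unscheduled, follow-up and early-termination results "will be mapped to a scheduled visit and will be used in the analysis only if the nominal scheduled visit result is missing". If several unscheduled or early-termination results share a window, "the one closest to the target date will be used".

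SAP 13.5 makes one exception for safety data: "all post-baseline assessments will be used for Potentially Clinically Significant (PCS) value determination and all assessments will be presented in the data listings". PCS values are defined in Table 2 of 7.2. Its highest ALT/AST cut is >3.0×ULN. Its combined criterion is ALT or AST >3×ULN with concurrent TBL >2.0×ULN. INR does not appear. Section 7.2 counts participants with post-baseline PCS values by arm and lists all laboratory values.

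Section 7.2 of the SAP addendum repeats the by-visit laboratory summaries through Week 52 and does not change these rules.

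**The concern.** The liver list in 7.2 grades severity more finely than Table 2, but its results are reported only visit by visit. This has two consequences.

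First, a peak found at an unscheduled test between two attended visits appears in no row of the liver table. Such tests are foreseeable: Protocol 11.1.9 requires clinically significant abnormal values to be followed with repeat tests until they resolve, stabilize or cease to matter clinically.

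Second, even without unscheduled tests, visit rows do not give the number of participants ever affected. One participant at ≥5×ULN at weeks 8 and 12 adds one to each row. Two different participants, one at each visit, produce the same rows.

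At stake is whether the report can state, per arm, how many participants ever reached the more severe liver categories. SAP 13.5 already accepts that threshold counts need every post-baseline value. The most severe liver thresholds fall outside that rule because they are not in Table 2.

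**Working it through.** The plan states no figure on this point, so there is none to reproduce. The check applies the rules as written.

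**1. Coverage of each category**

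| Liver category (7.2) | By-visit table (13.4 rule) | Any-time participant count (Table 2 with 13.5) |
|---|---|---|
| ALT/AST ≥3×ULN | Yes | Near-equivalent: >3.0×ULN |
| ≥3×ULN with TBL ≥2×ULN | Yes | Near-equivalent: >3×ULN with TBL >2.0×ULN |
| ≥3×ULN with INR ≥1.5 | Yes | None |
| ≥5×ULN | Yes | None; counted only as >3.0×ULN |
| >8×ULN | Yes | None; counted only as >3.0×ULN |

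**2. Three hypothetical participants (assumed values, SAP Table 5 windows)**

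- **A.** Unscheduled day 70: ALT 9×ULN, TBL 1×ULN, INR 1.6. All scheduled results are present and normal or near normal (ALT at most 1.2×ULN). Day 70 falls in the week 12 window (70 to <98), but the scheduled week 12 result exists, so the unscheduled one is not used. Liver table: 0 of 4 categories. PCS table: ALT >3×ULN counted; combined criterion not met, because TBL is normal and INR is not part of it. An any-time count would give 4 of 4.
- **B.** As A, but TBL 2.5×ULN and INR 1.0. Liver table: 0 of 4. PCS table: both ALT >3×ULN and ALT >3×ULN with TBL >2×ULN counted. An any-time count would give 4 of 4.
- **C.** Scheduled week 12 missing; unscheduled ALT 9×ULN on day 72 and 2×ULN on day 83, TBL and INR normal. Distances from target day 84 are 84 − 72 = 12 and 84 − 83 = 1, so day 83 is used. Liver table: 0 of 4. PCS table: ALT >3×ULN counted. An any-time count would give 3 of 4 (≥3×, ≥5×, >8×).

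In all three the participant appears in the PCS table, but no summary table shows that ALT exceeded 5× or 8×ULN. For A, none shows the INR criterion either.

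**3. How often an episode could fall between visits**

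From week 4 to week 24 of the randomized period, scheduled chemistry is 28 days apart (days 28, 56, 84, 112, 140, 168). The last gap, day 168 to day 182, is 14 days. Assume that an episode of d days starts at a uniformly random time in a gap of g days. The probability that it contains no scheduled visit is 1 − d/g for d < g, and 0 otherwise.

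| Episode length d (assumed) | g = 28 | g = 14 |
|---|---|---|
| 7 days | 1 − 7/28 = 75% | 1 − 7/14 = 50% |
| 14 days | 1 − 14/28 = 50% | 0% |
| 21 days | 1 − 21/28 = 25% | 0% |

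These are probabilities for an episode of given length. They are not expected counts.

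**The case against.** The strongest reply is that no affected participant disappears. Anyone at ≥5× or >8×ULN also exceeds 3×ULN and so enters the PCS count, which uses every post-baseline assessment. Raised transaminases with TBL >2×ULN are counted there too. Participants with a PCS value have their own listing, and all laboratory values are listed. Results judged clinically significant are also adverse events under Protocol 11.1.9, and the data monitoring committee sees cumulative laboratory data. All of this stands. A reader might infer from 7.2 and 13.4 that severe liver elevations are lost from the report or undercounted throughout. The documents do not support that. What is missing is the split above 3×ULN and the INR criterion, and adverse event tables do not grade by multiples of ULN.

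Second, 7.2 does not forbid an overall row, and the SAP Introduction places table specifications in a separate document not available here. That is fair, but the SAP does not require such a row.

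Third, the percentages rest on assumed durations and random onset. A repeat test prompted by an abnormal scheduled result would already leave the participant in some visit row, perhaps a lower one. This also stands. The documents do not show that peaks usually fall between visits, so the point does not rely on that.

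Fourth, the mismatch between ≥ in the liver list and > in Table 2 matters only at exact equality and carries no weight here.

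**Conclusion.** The point holds in a limited form. Followed as written, the SAP produces no summary table with the number of participants per arm who ever reached ALT/AST ≥5×ULN, >8×ULN, or ≥3×ULN with INR ≥1.5. Peaks in these categories can be absent from the liver table when they are found at unscheduled or early-termination tests, and the visit rows cannot be converted into participants ever affected. This conclusion rests on reading 7.2, 13.4, 13.5 and Table 2 together and needs no numerical assumption.

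The size is uncertain. The number of participants affected cannot be derived from the documents. The 75%, 50% and 25% figures only show how readily a short episode can fall between 28-day visits under random onset, and they are lower in the week 24 to 26 gap. Efficacy inference and error control are not touched. This is a gap in descriptive safety reporting that is worth closing because doing so costs almost nothing.

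**What to change.** In SAP 7.2, add for each of the four liver categories the number and percentage of participants who meet it at any post-baseline time, by treatment group and overall, using all scheduled and unscheduled results. For the combined category, require the ALT/AST and the TBL or INR results to be concurrent, and define what that means; Table 2 already asks for concurrent bilirubin. Extend the 13.5 exception to this table so that the 13.4 selection rule does not apply to it. The by-visit rows can stay.

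The addendum already revises some analyses of the randomized period, so it could carry this change too. Aligning the boundaries with Table 2 is optional tidying.

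The cost is one added any-time summary and short wording changes in 7.2 and 13.5. No new data are needed: ALT, AST, bilirubin and INR are all in the protocol's laboratory panel (Table 4).

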7. SELECTION AND WITHDRAWAL OF PARTICIPANTS

7.1. Inclusion Criteria

- 1. Aged at least 18 years; where approved, adolescents (aged 12-17 years) weighing at least 30 kg may also be enrolled.
- 2. A diagnosis of primary C3G or IC-MPGN (with or without previous renal transplant).
- 3. Evidence of active renal disease, based on one or more of the following:
 - a. In adults or adolescents with a baseline renal biopsy (either one collected during screening or a historic biopsy collected within 28 weeks prior to randomization), at least 2+ C3c staining on the baseline renal biopsy
 - b. In adolescents not providing a baseline renal biopsy, at least one of the following:
 - Plasma sC5b-9 level above the upper limit of normal during screening
 - Serum C3 below the lower limit of normal (LLN) during screening
 - Presence of an active urine sediment during screening, as evidenced by hematuria with at least 5 red blood cells per high-power field and/or red blood cell casts on routine local or central microscopic analysis of urine
 - Presence of C3 nephritic factor within 6 months of screening, based on central laboratory results or medical history
- 4. No more than 50% global glomerulosclerosis or interstitial fibrosis on the baseline biopsy for adult participants or adolescent participants providing a baseline biopsy.
- 5. At least 1 g/day of proteinuria on a screening 24-hour urine collection and a uPCR of at least 1000 mg/g in at least 2 FMU samples collected during screening.
- 6. eGFR ≥30 mL/min/1.73 m² calculated by the CKD-EPI creatinine equation for adults or the Bedside Schwartz equation for adolescents.
- 7. Stable regimen for C3G/IC-MPGN treatment, as described below:
 - a. Angiotensin-converting enzyme inhibitor, angiotensin receptor blocker, and/or sodium-glucose cotransporter-2 inhibitor therapy that is stable and optimized, in the opinion of the investigator, for at least 12 weeks prior to randomization
 - b. Stable doses of other medications that can affect proteinuria (eg, steroids, mycophenolate mofetil, and/or other allowed immunosuppressants that the participant is receiving for treatment of C3G or IC-MPGN) for at least 12 weeks prior to randomization.
 - c. If a participant is on prednisone (or other systemic corticosteroid) for C3G or IC-MPGN treatment, the dosage is stable and no higher than 20 mg/day (or equivalent dosage of a corticosteroid other than prednisone) for at least 12 weeks prior to randomization.

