8.3.2. Rescue Therapy

In the event of an increase in serum creatinine to at least 2× the baseline level that in the opinion of the investigator is due to the underlying C3G/IC-MPGN disease, rescue therapy may be considered, such as high-dose corticosteroids and/or C5 inhibitor treatment.

If the participant receives rescue therapy that is not a prohibited concomitant medication, then they will be allowed to remain on study drug. If a participant receives rescue therapy that is a prohibited concomitant medication, they will be discontinued from study drug, as described in Section 8.3.3.

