11.2.4. Pregnancy

Although pregnancy is not an AE, all pregnancies and suspected pregnancies (including a positive pregnancy test regardless of the pregnant person's age or disease state) occurring with a female participant or the female partner of a male participant must be followed to conclusion to determine their outcome and are considered immediately reportable events.

Any pregnancy, suspected pregnancy, or positive pregnancy test must be reported to Apellis Safety within 24 hours of the investigator or their representative becoming aware of the event, using the pregnancy report form. The pregnancy report form must be signed and dated by the investigator and submitted via email to [contact].

The investigator should make every effort to obtain the consent from the pregnant woman to follow the status of the pregnancy until completion. The outcome of the pregnancy (eg, delivery, termination) and, as applicable, the neonatal outcome should be reported within 24 hours of awareness. In the event of an abnormal outcome (outcome other than live, healthy birth), an SAE report form must be reported within 24 hours of investigator awareness, as described in Section 11.2.3.

11.2.5. **AEs of Special Interest**

The following events are classified as AEs of special interest:

- Thrombocytopenia
- Severe infection (see Section 11.2.2.2 for a discussion of severity grading)
- Hypersensitivity, including pneumonitis
- Severe acute kidney injury (see Section 11.2.2.2 for a discussion of severity grading)

An AE of special interest can be serious or nonserious but must be reported to the sponsor/Apellis Safety in the same manner as an SAE, as described in Section 11.2.3.

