6.4.4. Subgroup Analyses of Primary Efficacy Endpoint

Subgroup analyses will be performed to evaluate the consistency of the primary analysis results across subgroups defined by demographic and baseline characteristics. Analyses will be performed for the primary efficacy endpoint for each of the following subgroups (as appropriate per actual subgroup sample size, levels with low sample size may be pooled to allow for an analysis to be conducted):

- Age group: adolescent, adult
- Sex: male, female
- Race: Caucasian, non-Caucasian
- Geographic region: United States, Rest of World
- Disease type: C3G, IC-MPGN
- Transplant history: nontransplant, posttransplant
- Baseline FMU uPCR: <3000 mg/g, ≥3000 mg/g
- Baseline eGFR: <60 mL/min/1.73 m², >60 mL/min/1.73 m²
- Baseline C3 level: normal, below the LLN
- Baseline immunosuppressants use: yes, no (based on ATC level 2 of "IMMUNOSUPPRESSANTS" and/or "CORTICOSTEROIDS FOR SYSTEMIC USE")

The estimated treatment effects and corresponding 95% CIs and p-values from the models will be displayed graphically for each level of the subgroups specified via forest plots.

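### SAP 7.2: the creatinine flag ignores baseline, and rescaling of local laboratory values does not preserve multiples of the upper limit of normal

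*SAP*

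**What the plan says.** Three provisions of SAP 7.2 matter here.

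- **PCS rule.** Table 2 sets numerical limits for haematology and liver tests. Creatinine has none; instead, for "creatinine; LDH; creatine kinase (CK); uric acid; glucose; sodium; potassium; and chloride, abnormal values will be used as potentially clinically significant". The count is then defined: "The number and percentage of participants with post-baseline PCS laboratory values will be tabulated by treatment group and overall". Neither sentence asks for a normal baseline or a worsening.
- **Rescaling.** When COVID-19 leads to a local laboratory being used in place of the central one, "all local laboratory values will be standardized to a central laboratory value using the following formula". The formula is X_S = L_S + (U_S − L_S)/(U_X − L_X) × (X − L_X), where L and U are the lower and upper normal limits, the subscript X is local and S is central. A further specification is promised. The problems it names are absent ranges and negative results.
- **Liver flags.** The by-visit summary uses ALT or AST at ≥3×, ≥5× and >8× ULN, and ≥3× together with bilirubin ≥2× ULN or INR ≥1.5. Table 2 adds ULN multiples for ALT, AST, ALP, bilirubin and GGT. The section does not say whether the multiple is taken before or after rescaling.

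On the population, Protocol 7.1 requires "eGFR ≥30 mL/min/1.73 m² calculated by the CKD-EPI creatinine equation for adults", with the Bedside Schwartz equation for adolescents. SAP 6.4.4 plans subgroups by "Baseline eGFR: <60 mL/min/1.73 m², >60 mL/min/1.73 m²", so eGFR below 60 at entry is expected.

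**The concern.** A participant whose creatinine was high before the first dose and never moves is counted in the same way as one whose creatinine has newly doubled. The row then largely reflects kidney function at entry, which randomisation spreads over both arms, and a difference in new rises is diluted. The SAP does use baseline elsewhere: Table 3 includes rises and falls in blood pressure, and Table 4 includes QTcF increases. Severe acute kidney injury is an adverse event of special interest (Protocol 11.2.5), so a safety reader would look for a by-arm count of individual creatinine rises. No planned table gives one.

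The liver flags are thresholds on a ratio to ULN. A transformation that changes this ratio can move a participant across a threshold in either direction, including in the combined ALT/AST and bilirubin rule.

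**Working it through.** The plan states no figure on this point, so there is none to reproduce. The two parts are independent.

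**Creatinine: who is flagged.** The only eGFR equation written out in the documents is Bedside Schwartz (Protocol 6.1.1). Rearranged, creatinine = 0.413 × height / eGFR. At an assumed height of 160 cm this is 66.08 / eGFR: 2.20 mg/dL at eGFR 30, 1.47 at 45 and 1.10 at 60. With an assumed ULN of 0.8, 1.0, 1.2 or 1.3 mg/dL, creatinine exceeds ULN at any eGFR below about 83, 66, 55 or 51. A stable adolescent in that range is flagged with no change from baseline. The adult equation is not written out, so no adult figure is computed.

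**Creatinine: dilution.** Let b be the share abnormal at baseline (assumed equal in both arms and still abnormal at some later visit), and p the rate of new abnormality, assumed unrelated to baseline status. The PCS rate is b + (1 − b)p, and the between-arm difference is (1 − b)(p₁ − p₀). With assumed p of 10% and 2%, a true difference of 8 points:

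| b (assumed) | arm with p = 10% | arm with p = 2% | difference shown |
|---|---|---|---|
| 30% | 0.30 + 0.70×0.10 = 37.0% | 0.30 + 0.70×0.02 = 31.4% | 5.6 points |
| 50% | 55.0% | 51.0% | 4.0 points |
| 70% | 73.0% | 70.6% | 2.4 points |

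The shrinkage factor 1 − b is the same whatever pair of rates is assumed.

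**Rescaling.** Let m = X/U_X (the multiple of local ULN), a = L_X/U_X and s = L_S/U_S. Dividing the SAP formula by U_S gives

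X_S/U_S = s + (1 − s)(m − a)/(1 − a) = 1 + k(m − 1), with k = (1 − s)/(1 − a).

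At m = 1 the result is 1, and at m = a it is s. Normal or abnormal status is therefore unchanged, and so is the creatinine flag. Multiples survive only if k = 1, that is a = s (including both lower limits zero). Otherwise a flag at t fires from a local multiple of 1 + (t − 1)/k. On assumed ratios:

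| a (local) | s (central) | k | local 3× reads as | needed for 3× | needed for 5× | needed for 8× | needed for bilirubin 2× |
|---|---|---|---|---|---|---|---|
| 0 | 0.1 | 0.90 | 2.80 | 3.22 | 5.44 | 8.78 | 2.11 |
| 0 | 0.2 | 0.80 | 2.60 | 3.50 | 6.00 | 9.75 | 2.25 |
| 0 | 0.3 | 0.70 | 2.40 | 3.86 | 6.71 | 11.0 | 2.43 |
| 0.1 | 0 | 1.11 | 3.22 | 2.80 | 4.60 | 7.30 | 1.90 |
| 0.2 | 0 | 1.25 | 3.50 | 2.60 | 4.20 | 6.60 | 1.80 |
| 0.3 | 0 | 1.43 | 3.86 | 2.40 | 3.80 | 5.90 | 1.70 |

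- Flag missed: local 0–40, central 10–50, ALT 130. Locally 130/40 = 3.25×. Rescaled: 10 + (40/40)×130 = 140, and 140/50 = 2.80×.
- Flag created: local 10–50, central 0–40, ALT 135. Locally 135/50 = 2.70×. Rescaled: (40/40)×(135 − 10) = 125, and 125/40 = 3.12×.

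**Creatinine fold-changes.** On assumed ranges of 62–106 (local) and 53–115 (central) µmol/L, a value of 150 becomes 53 + (62/44)×(150 − 62) = 177, which is 18% higher. Both are above ULN, so no planned flag moves. A count of rises from a central baseline would, however, be distorted.

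**The case against.** **Renal deterioration is reported elsewhere.** A reader might infer that the plan hides or misreports kidney injury. The documents do not support that. SAP 7.2 summarises creatinine and its change from baseline by visit, with minimum and maximum (SAP 13.1). SAP 6.5.5.1 does the same for eGFR and adds a repeated-measures model. SAP 6.5.1.1 breaks down the composite endpoint, which shows eGFR falls above 15% at week 26. SAP 7.1 tabulates events of special interest, and all laboratory values are listed. PCS is a screening label.

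This stands, but none of these outputs counts individual creatinine rises by arm. The week 26 breakdown is a single time point with intercurrent events set to non-response. The eGFR model replaces values after rescue or dialysis by imputation. The special-interest event needs an investigator grading of severe on a general scale.

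**The 2× multiple is not a safety criterion.** Protocol 8.3.2 uses an "increase in serum creatinine to at least 2× the baseline level" as a condition for considering rescue, when the investigator attributes it to the underlying disease. That is correct, so here it can serve only as a reporting cut.

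**Rescaling is narrow and its use is not settled.** It is described only for COVID-19 local testing. Protocol Appendix 3 prefers the central laboratory and keeps screening, day 1 and week 26 visits in clinic. SAP 7.2 also opens by classifying results on ranges supplied by local laboratories, and the promised specification could resolve the matter. A reader might infer that every locally tested participant's liver flags shift, or that rescaling alters the creatinine flag. Neither follows from the formula. What remains is that the rescaling sentence covers local values without exception, and ULN multiples are not among the problems named for the later specification.

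**Conclusion.** Both defects follow from the SAP text, and they are separate. The creatinine PCS row is non-specific in this population and dilutes a difference in new rises by the factor 1 − b. The linear map can create or remove ULN-multiple flags for locally tested participants, provided that flags use the rescaled value (the natural reading, though not an explicit one) and that LLN/ULN differs between the laboratories.

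The size is unknown. Every baseline rate, injury rate, height and reference range used above is an assumption, and the documents give no share of local samples. If injury is commoner among those already abnormal at entry, the dilution is greater than shown; if some of them later return to normal, it is smaller. No efficacy or type I error conclusion is affected.

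**What to change.** 1. In SAP 7.2, tabulate by arm the participants with any post-baseline creatinine at least 2× baseline, optionally with a lower cut. The lower cut would be an added analysis choice with no source in the documents. Label the 2× cut as a reporting threshold with no bearing on the rescue rule. For creatinine and the other seven analytes, count an abnormal value only if it is new or worse than baseline.
2. State that every ULN-multiple criterion uses the reported value divided by the reporting laboratory's own ULN. The factor k then drops out, and a local 3.0× stays 3.0× for any pair of ranges. Use unit conversion only, without range rescaling, for creatinine fold-changes.

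The cost is SAP wording and minor extra derivations, with no new data. SAP addendum 7.2 refers back to this section, so the same wording would carry to week 52. The drawback is that by-visit means still mix laboratories.
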